#### CALCULATIONS

For the first question, weekly frequencies of strenuous, moderate, and light activities are multiplied by nine, five, and three, respectively. Total weekly leisure activity is calculated in arbitrary units by summing the products of the separate components, as shown in the following formula:

Weekly leisure activity score = (9 × Strenuous) + (5 × Moderate) + (3 × Light)

The second question is used to calculate the frequency of weekly leisure-time activities pursued "long enough to work up a sweat" (see questionnaire).

EXAMPLE

Strenuous = 3 times/wk

Moderate = 6 times/wk

Light = 14 times/wk

Total leisure activity score =  $(9 \times 3) + (5 \times 6) + (3 \times 14) = 27 + 30 + 42 = 99$ 

### Godin Leisure-Time Exercise Questionnaire

 During a typical 7-Day period (a week), how many times on the average do you do the following kinds of exercise for more than 15 minutes during your free time (write on each line the appropriate number).

		Times Per
		Week
a)	STRENUOUS EXERCISE	
	(HEART BEATS RAPIDLY)	
	(e.g., running, jogging, hockey, football, soccer,	
	squash, basketball, cross country skiing, judo,	
	roller skating, vigorous swimming,	
	vigorous long distance bicycling)	
b)	MODERATE EXERCISE	
	(NOT EXHAUSTING)	
	(e.g., fast walking, baseball, tennis, easy bicycling,	
	volleyball, badminton, easy swimming, alpine skiing,	
	popular and folk dancing)	
c)	MILD EXERCISE	
	(MINIMAL EFFORT)	
	(e.g., yoga, archery, fishing from river bank, bowling,	
	horseshoes, golf, snow-mobiling, easy walking)	

2. During a typical 7-Day period (a week), in your leisure time, how often do you engage in any regular activity long enough to work up a sweat (heart beats rapidly)?

OFTEN	SOMETIMES	NEVER/RARELY
1. 0	2. 🛛	3. 🛛

# 19.11 Appendix K: Trails Making Test (TMT) Parts A & B

# Trail Making Test (TMT) Parts A & B

#### Instructions:

Both parts of the Trail Making Test consist of 25 circles distributed over a sheet of paper. In Part A, the circles are numbered 1 - 25, and the patient should draw lines to connect the numbers in ascending order. In Part B, the circles include both numbers (1 - 13) and letters (A - L); as in Part A, the patient draws lines to connect the circles in an ascending pattern, but with the added task of alternating between the numbers and letters (i.e., 1-A-2-B-3-C, etc.). The patient should be instructed to connect the circles as quickly as possible, without lifting the pen or pencil from the paper. Time the patient as he or she connects the "trail." If the patient makes an error, point it out immediately and allow the patient to correct it. Errors affect the patient's score only in that the correction of errors is included in the completion time for the task. It is unnecessary to continue the test if the patient has not completed both parts after five minutes have elapsed.

Step 1:	Give the patient a copy of the Trail Making Test Part A worksheet and a pen or pencil.
Step 2:	Demonstrate the test to the patient using the sample sheet (Trail Making Part A – SAMPLE).
Step 3:	Time the patient as he or she follows the "trail" made by the numbers on the test.
Step 4:	Record the time.

Step 5: Repeat the procedure for Trail Making Test Part B.

### Scoring:

Results for both TMT A and B are reported as the number of seconds required to complete the task; therefore, higher scores reveal greater impairment.

	Average	Deficient	Rule of Thumb
Trail A	29 seconds	> 78 seconds	Most in 90 seconds
Trail B	75 seconds	> 273 seconds	Most in 3 minutes

# Trail Making Test Part A – SAMPLE

-Total time to complete in seconds: \_\_\_\_\_\_ - Number of errors: \_\_\_\_\_

# Trail Making Test Part B – SAMPLE

# 19.12 Appendix L: HVLT-R Forms 1, 2 and 3

# HVLT-R

# Form 1

# **Test Booklet**

[name] [name]

PAR • [name] • [name] • www.parinc.com

Copyright @ 1991, 1998, 2001 by PAR. All rights reserved. May not be reproduced in whole or in part in any form or by any means without written permission of PAR. This form is printed in teal ink on white paper. Any other version is unauthorized. 98

Reorder #RO-4753

Printed in the U.S.A.

WARNING! PHOTOCOPYING OR DUPLICATION OF THIS FORM WITHOUT PERMISSION IS A VIOLATION OF COPYRIGHT LAWS.

### Learning Trial Instructions

Trial 1

Say the following:

I am going to read a list of words to you. Listen carefully, because when I'm through, I'd like you to tell me as many of the words as you can remember. You can tell them to me in any order. Are you ready?

- Repeat or paraphrase the instructions if necessary.
- Read the words at the rate of approximately one word every 2 seconds.
- If the individual does not spontaneously begin reporting words after the last word is read, say the following:

### OK. Now tell me as many of those words as you can remember.

Record the responses verbatim (including repetitions and intrusions) in the Trial 1 column. When the individual indicates no more words can be recalled, proceed to Trial 2.

### Trial 2

Say the following:

Now we are going to try it again. I am going to read the same list of words to you. Listen carefully, and tell me as many of the words as you can remember, in any order, including all the words you told me the first time.

Use the same procedure as in Trial 1 to record the responses in the column for Trial 2. Then proceed to Trial 3.

### Trial 3

Say the following:

I am going to read the list one more time. As before, I'd like you to tell me as many of the words as you can remember, in any order, including all the words you've already told me.

Record the responses in the column for Trial 3 using the same procedure as in the previous trials. NOTE: Do not tell the respondent that recall of the words will be tested later.

### **Delayed Recall Trial Instructions**

After the 20-25 minute delay, say the following:

Do you remember that list of words you tried to learn before?

If the response is "No," remind the individual that you read the list three times and that he or she was asked to recall the words each time. Say the following:

Tell me as many of those words as you can remember.

# Form 1

Semantic Categories: Four-Legged Animals, Precious Stones, Human Dwellings

Word List		Learning Trials		Delayed Recal Trial (20-25 min.
LION	Trial 1	Trial 2	Trial 3	Trial 4
EMERALD				
HORSE				3
TENT				
SAPPHIRE				
HOTEL				
CAVE				
OPAL				
TIGER				
PEARL				
COW				
HUT				
Total correct responses =				
			Completion Time Trial 3	Start Time Trial 4

### **Delayed Recognition Trial Instructions**

The Delayed Recognition (Forced Choice) trial is administered immediately after the Delayed Recall trial. Say the following:

Now I am going to read a longer list of words to you. Some of them are words from the original list, and some are not. After I read each word, I'd like you to say "Yes" if it was on the original list, or "No" if it was not.

Read the words of the Delayed Recognition trial list in numerical order. Allow the individual as much time as needed to respond. You may use the prompt, **"Was horse on the list? Yes or no?"** The individual must give you a response for every word. If the individual is not sure, ask for a guess.

	Delayed Recognition Trial (Forced Choice)														
1.	HORSE	Υ	Ν	7.	house	Y	Ν	13.	HUT	Y	Ν	19.	TENT	Y	N
2.	ruby	Y	Ν	8.	OPAL	Y	Ν	14.	EMERALD	Y	Ν	20.	mountain	Y	Ν
З.	CAVE	Υ	N	9.	TIGER	Y	Ν	15.	SAPPHIRE	Y	Ν	21.	cat	Y	N
4.	balloon	Y	N	10.	boat	Y	Ν	16.	dog	Y	Ν	22.	HOTEL	Y	N
5.	coffee	Y	N	11.	scarf	Y	Ν	17.	apartment	Y	Ν	23.	COW	Y	Ν
6.	LION	Y	N	12.	PEARL	Y	N	18.	penny	Y	Ν	24.	diamond	Y	Ν

Total number of true-positive responses ("hits"): \_\_\_\_\_ /12 (no shading)

Semantically-related false-positive errors: \_\_\_\_\_/6 (light shading) Semantically-unrelated false-positive errors: \_\_\_\_\_/6 (darker shading) Total number of false-positive errors: \_\_\_\_\_/12

	Raw score	T score
Total Recall (sum of total correct responses for Trials 1, 2, & 3)		
Delayed Recall (Trial 4)		
Retention (%) [(Trial 4 ÷ Higher score of Trials 2 and 3) x 100]		
Recognition Discrimination Index (Total no. of true-positives) - (Total no. of false-positives)		

Normative table (Appendix A): \_\_\_\_\_

# HVLT-R

# Test Booklet

[name] [name]

PAR • [name] • [name] • www.parinc.com

Copyright © 1991,1998, 2001 by PAR. All rights reserved. May not be reproduced in whole or in part in any form or by any means without written permission of PAR. This form is printed in burgundy ink on white paper. Any other version is unauthorized. 9 8 7 6 5 Reorder #RO-4754 Printed in the U.S.A.

WARNING! PHOTOCOPYING OR DUPLICATION OF THIS FORM WITHOUT PERMISSION IS A VIOLATION OF COPYRIGHT LAWS.

### Learning Trial Instructions

Trial 1

Say the following:

I am going to read a list of words to you. Listen carefully, because when I'm through, I'd like you to tell me as many of the words as you can remember. You can tell them to me in any order. Are you ready?

- Repeat or paraphrase the instructions if necessary.
- Read the words at the rate of approximately one word every 2 seconds.
- If the individual does not spontaneously begin reporting words after the last word is read, say the following:

### OK. Now tell me as many of those words as you can remember.

Record the responses verbatim (including repetitions and intrusions) in the Trial 1 column. When the individual indicates no more words can be recalled, proceed to Trial 2.

### Trial 2

Say the following:

Now we are going to try it again. I am going to read the same list of words to you. Listen carefully, and tell me as many of the words as you can remember, in any order, including all the words you told me the first time.

Use the same procedure as in Trial 1 to record the responses in the column for Trial 2. Then proceed to Trial 3.

### Trial 3

Say the following:

I am going to read the list one more time. As before, I'd like you to tell me as many of the words as you can remember, in any order, including all the words you've already told me.

Record the responses in the column for Trial 3 using the same procedure as in the previous trials. **NOTE:** Do not tell the respondent that recall of the words will be tested later.

### **Delayed Recall Instructions**

After the 20-25 minute delay, say the following:

Do you remember that list of words you tried to learn before?

If the response is "No," remind the individual that you read the list three times and that he or she was asked to recall the words each time. Say the following:

Tell me as many of those words as you can remember.

1	Learning Trials Trial 2	Date Trial 3	Delayed Reca (20-25 min.) Trial 4
1	Learning Trials Trial 2	Trial 3	Delayed Reca (20-25 min.) Trial 4
1	Trial 2	Trial 3	Trial 4
			1
		_	
		-	

### Delayed Recognition Instructions

The Delayed Recognition (Forced Choice) trial is administered immediately after the Delayed Recall trial. Say the following:

Now I am going to read a longer list of words to you. Some of them are words from the original list, and some are not. After I read each word, I'd like you to say "Yes" if it was on the original list, or "No" if it was not.

Read the words of the Delayed Recognition trial list in numerical order. Allow the individual as much time as needed to respond. You may use the prompt, **"Was spoon on the list? Yes or no?"** The individual must give you a response for every word. If the individual is not sure, ask for a guess.

	Delayed Recognition (Forced Choice)														
1.	spoon	Y	Ν	7.	harmonica	Y	Ν	13.	knife	Y	Ν	19.	WINE	Y	Ν
2.	PISTOL	Y	N	8.	can opener	Y	Ν	14.	RUM	Υ	Ν	20.	lemon	Y	Ν
3.	doll	Y	Ν	9.	SWORD	Y	Ν	15.	trout	Y	Ν	21.	SPATULA	Y	Ν
4.	whiskey	Y	Ν	10.	pencil	Y	Ν	16.	BOMB	Y	Ν	22.	BOURBON	Y	Ν
5.	FORK	Y	Ν	11.	gun	Y	N	17.	PAN	Y	Ν	23.	beer	Y	Ν
6.	POT	Y	Ν	12.	VODKA	Y	Ν	18.	gold	Y	Ν	24.	RIFLE	Y	Ν

Total number of true-positive responses ("hits"): \_\_\_\_\_ /12 (no shading)

Total number of false-positive errors:	/12
Semantically-unrelated false-positive errors:	/6 (darker shading)
Semantically-related false-positive errors:	/6 (light shading)

	Raw score	7 score
Total Recall (sum of total correct responses for Trials 1, 2, & 3)		
Delayed Recall (Trial 4)		
Retention (%) [(Trial 4 ÷ Higher score of Trials 2 and 3) x 100]		
Recognition Discrimination Index (Total no. of true-positives) - (Total no. of false-positives)		

Normative table (Appendix A): \_\_\_\_\_

# HVLT-R

# Test Booklet

[name] [name]

PAR • [name] • [name] • www.parinc.com

Copyright © 1991,1998, 2001 by PAR. All rights reserved. May not be reproduced in whole or in part in any form or by any means without written permission of PAR. This form is printed in blue ink on white paper. Any other version is unauthorized. 9 8 7 6 Reorder #RO-4755 Printed in the U.S.A.

WARNING! PHOTOCOPYING OR DUPLICATION OF THIS FORM WITHOUT PERMISSION IS A VIOLATION OF COPYRIGHT LAWS.

### Learning Trial Instructions

Trial 1

Say the following:

I am going to read a list of words to you. Listen carefully, because when I'm through, I'd like you to tell me as many of the words as you can remember. You can tell them to me in any order. Are you ready?

Repeat or paraphrase the instructions if necessary.

- Read the words at the rate of approximately one word every 2 seconds.
- If the individual does not spontaneously begin reporting words after the last word is read, say the following:

OK. Now tell me as many of those words as you can remember.

Record the responses verbatim (including repetitions and intrusions) in the Trial 1 column. When the individual indicates no more words can be recalled, proceed to Trial 2.

#### Trial 2

Say the following:

Now we are going to try it again. I am going to read the same list of words to you. Listen carefully, and tell me as many of the words as you can remember, in any order, including all the words you told me the first time.

Use the same procedure as in Trial 1 to record the responses in the column for Trial 2. Then proceed to Trial 3.

### Trial 3

Say the following:

I am going to read the list one more time. As before, I'd like you to tell me as many of the words as you can remember, in any order, including all the words you've already told me.

Record the responses in the column for Trial 3 using the same procedure as in the previous trials. **NOTE:** Do not tell the respondent that recall of the words will be tested later.

### **Delayed Recall Instructions**

After the 20-25 minute delay, say the following:

#### Do you remember that list of words you tried to learn before?

If the response is "No," remind the individual that you read the list three times and that he or she was asked to recall the words each time. Say the following:

Tell me as many of those words as you can remember.

# Form 3

# Semantic Categories: Musical Instruments, Fuels, Food Flavorings

Word List		Learning Trials		Delayed Reca
monurlin			C	(20-25 min.)
SUGAR	Trial 1	Trial 2	Trial 3	Trial 4
TRUMPET				
VIOLIN				
COAL				
GARLIC				
KEROSENE				
VANILLA				
WOOD				
CLARINET				
FLUTE				
CINNAMON				
GASOLINE				8
Total correct responses =				
			Completion Time	Start Time

### **Delayed Recognition Instructions**

The Delayed Recognition (Forced Choice) trial is administered immediately after the Delayed Recall trial. Say the following:

Now I am going to read a longer list of words to you. Some of them are words from the original list, and some are not. After I read each word, I'd like you to say "Yes" if it was on the original list, or "No" if it was not.

Read the words of the Delayed Recognition trial list in numerical order. Allow the individual as much time as needed to respond. You may use the prompt, **"Was pepper on the list? Yes or no?"** The individual must give you a response for every word. If the individual is not sure, ask for a guess.

	Delayed Recognition (Forced Choice)									
1.	pepper	ΥN	7. ball	ΥN	13. TRUMPET Y N 19. KEROSENE Y I	N				
2.	GARLIC	ΥN	8. salt	ΥN	14. basement Y N 20. VANILLA Y I	N				
3.	WOOD	ΥN	9. priest	ΥN	15. CINNAMON Y N 21. GASOLINE Y I	N				
4.	drum	ΥN	10. chair	YN	16. FLUTE Y N 22. sand Y I	N				
5.	oil	ΥN	11. COAL	ΥN	17. electricity Y N 23. piano Y I	N				
6.	SUGAR	ΥN	12. CLARINET	ΥN	18. moon Y N 24. VIOLIN Y I	N				

Total number of true-positive responses ("hits"): \_\_\_\_\_ /12 (no shading)

Semantically-related false-positive errors: \_\_\_\_\_\_/6 (light shading)

Semantically-unrelated false-positive errors: \_\_\_\_\_\_ /6 (darker shading)

Total number of false-positive errors:

	Raw score	T score
Total Recall (sum of total correct responses for Trials 1, 2, & 3)		
Delayed Recall (Trial 4)		
Retention (%) [(Trial 4 ÷ Higher score of Trials 2 and 3) x 100]		
Recognition Discrimination Index (Total no. of true-positives) - (Total no. of false-positives)		

\_\_\_\_\_/12

Normative table (Appendix A): \_\_\_\_\_

# 19.1 Appendix M: COWA

Multilingual Aphasia Examination III – Controlled Oral Word Association Arthur Benton, Kerry deS. Hamsher, and Abigail Sivan			Record Sheet		
Vame		No	Date/		
ge Gender	Educatio	on (no. of years) Handedness	month day year Examiner		
First Letter C (Form A)	r (1 minute) or P (Form B)	Second Letter (1 minute) F or R (Form A) (Form B)	Third Letter (1 minute) L or W (Form A) (Form B)		
1					
2					
3					
ł					
·					
	n				
			4		
			T		
No. of correct respo	+	No. of correct responses +	No. of correct responses =		
Total Raw Score	+ Adjustmer (see table)	nt = Adjusted Score	(from manual)		
Adjustmen	t Age (years)	emarks:			
lucation (years) 25-5	4 55-59 60-69				
9-11 = 5 12-15 = 3	7 9 4 6				
• [name] • [name] • www.par	INC.COM		
m white paper. Any other vers	sion is unauthorized.	www.m.whole or an part in dry form of by any filearts w	move, white permeetor of 24th, this furthe pitting in t		

4.		
	WARNING! PHOTOCOPYING OR DUPLICATION OF THIS FORM WIT	HOUT PERMISSION IS A VIOLATION OF COPYRIGHT LAWS.

FDA	Food and Drug Administration
Gy	Gray
HGG	High Grade Glioma
HRQoL	Health related Quality of Life
HVLT-R	Hopkins Verbal Learning Test - Revised
ICH	International Conference on Harmonization
ITT	Intent to Treat
os	Overall Survival
PFS	Progression Free Survival
PK	Pharmacokinetic
PRO	Patient Reported Outcome
RANO	Response Assessment in Neuro-Oncology
RT	Radiation Therapy
SAE	Serious Adverse Event
SAP	Statistical Analysis Plan
SOC	Standard of Care
TEAE	Treatment-Emergent Adverse Event
TMT	Trails Making Test
TMZ	Temozolomide
WHO	World Health Organization

3 INTRODUCTION

This Statistical Analysis Plan (SAP) is based on the current trial protocol (version 9.0 dated 25 May 2019). If statistical methods differ substantially between the SAP and the protocol, refer to the SAP.

The SAP describes the datasets and the statistical methods to be used for reporting and analysis of all data collected during the trial.

If a future protocol amendment necessitates a substantial change to the statistical analysis of the trial data, the SAP will be amended. If, after the database is locked, additional analyses are required to supplement the planned analyses described in this SAP, those unplanned analyses will not be described in an amended SAP, but they will be identified in the final Clinical Study Report (CSR).

We have considered the following guidelines when writing this SAP:

- International Conference on Harmonization (ICH) E9, Guidance for Industry: Statistical Principles for Clinical Trials
- ICH E3, Guidance for Industry: Structure and Content of Clinical Study Reports.

Statistical analysis will primarily be conducted using SAS version 9.4, with additional analyses and data visualization performed using the R software (version 4.2.1 or later).

4 OVERVIEW OF STUDY DESIGN

The Phase 2 portion of this protocol is a multicenter randomized open-label study comparing the impact of concurrent daily Temozolomide (TMZ) and Radiation Therapy (RT) with BMX-001 (Arm A) versus concurrent daily TMZ and RT alone (Arm B) on survival in patients among patients with newly diagnosed high grade glioma (HGG - WHO grade III and IV). Subjects were randomized with a treatment arm allocation ratio

TREATMENT ARMS

Arm A: Concurrent daily TMZ and RT with BMX-001

Arm B: Concurrent daily TMZ and RT alone

of 1:1, with a goal of enrolling 160 patients in this phase of the study (80 subjects per arm). A permuted block randomization stratified by histologic grade (grade III / IV) and institution will be used to assign patients to treatment with or without BMX-001.

Subjects in Arm A were administered BMX-001 subcutaneously first as a loading dose (28 mg) given 0 to 4 days before the start of chemoradiation and then at subsequent dose (14 mg) twice a week for eight weeks. Subjects in Arm A and Arm B received TMZ dosed at 75 mg/m² orally daily for 42 days and RT delivered in daily fractions of 1.8-2 Gy given 5 days a week for 6 weeks for a total of 59.4-60 Gy.

In all subjects, cognitive performance was measured at the time of enrollment and 2 weeks after the completion of RT, and standard of care (SOC) clinic visits (approximately 8 weeks apart +/- 2 weeks) until death, or patient's choice to discontinue study measures. Cognitive testing was to continue after noted progression until the 12 month follow up timepoint is reached.

In order to characterize the repeated dose pharmacokinetic (PK) profiles of BMX-001 in combination with RT and TMZ in newly diagnosed HGG patients, PK blood samples were drawn on Days 8 and 36 only from the first 6 patients enrolled and assigned to Arm A at a single center (Duke). Measures were obtained at approximately the following times: Pre-

dose, then 0.5 hour, 1 hour, 2 hours, 6 hours and 24 hours post-dose. Samples will be analyzed for BMX-001 using validated analytical methods at the Duke PK lab.

The study's primary phase 2 endpoint is overall survival (OS), defined as the time between randomization and death. A logrank test will be used to compare the survival experience of the two treatment arms. An intent-to-treat philosophy will be used in the analysis of survival by including all patients who are randomized in the analysis. Other analysis sets are defined in this document.

Among the secondary endpoints are two that are of particular interest: cognitive function and thrombocytopenia. The mean change in cognitive functioning between baseline (enrollment) and week 24 within each treatment arm will be computed, and analysis of covariance will be conducted to compare groups with respect to that change. Treatment group assignment will be included in the model as a predictor, and the baseline measure of cognitive function will be included as a covariate.

The proportion of patients who experience grade 3 or 4 thrombocytopenia during concurrent temozolomide and radiation, a period that terminates 2 weeks after completion of radiation treatment, will be summarized. A chi-square test will be conducted to compare the prevalence of such thrombocytopenia observed in patients with and without BMX-001.

5 PATIENT CHARACTERISTICS

The clinical and socio-demographic characteristics of all randomized patients will be summarized using descriptive statistics (e.g., means/standard deviations, percentiles, frequencies). Patient characteristics will be summarized by treatment group assignment. Characteristics that will be summarized include:

- Institution
- Race
- Ethnicity
- Gender
- Tumor Grade, according to WHO grade at time of enrollment and WHO 2021^{1*}
- Performance Status (KPS)
- Histology
- Disease Description (Unifocal / Multifocal)
- MGMT Status (Methylated / Unmethylated)
- IDH: mutated or wildtype
- Extent of Resection (Gross total Resection / Subtotal Resection / Biopsy Only)
- Age

6 ANALYSIS POPULATIONS

The following populations will be identified:

• Intent to Treat Population (ITT): All patients randomized into the clinical trial, regardless of compliance.

¹ During study accrual, a new WHO classification system for CNS tumors was published [1]. Though the classification system in use at the time of study activation was used throughout the conduct of the study, the classification of all patients under the new WHO 2021 system will also be described.

- Safety Population: All patients who received at least one dose of BMX-001 or temozolomide
- Treated Population: All patients who completed chemoradiation with or without BMX-001. BMX-001 must be given for at least 6 weeks (or 13 doses).
- PK Population: Subjects who participated in the PK portion of the study (n=6).

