### 9.1.5 Missed Doses

Regardless of the reason for withholding study drug treatment, the maximum allowable length of treatment interruption is 3 weeks. If BMX-001 is withheld for greater than 3 weeks, BMX-001 will be discontinued. If BMX-001 is discontinued for missed doses, the patient will remain on the study and all planned study endpoints will be assessed. Any missed doses should be made up at the end of treatment, so that the subjects complete the planned number of doses (which is 17). Any missed doses of BMX-001 should be documented with the reason included.

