#### Hematologic Criteria

- 1. Grade 4 neutropenia (ANC, including bands,  $\leq$  500 cells /µl);
- 2. Grade 3 thrombocytopenia (platelet count of  $\leq$  50,000 cells/µl);

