# 16.1 Analysis Sets

MTD Analysis Set: Patients who complete concurrent chemoradiation with scheduled treatments with BMX-001 or terminate treatment during that period of time due to DLT will be considered evaluable and included in the analysis of MTD.

Adverse Experience Analysis Set: All patients who receive BMX-001 will be included in any overall summary of adverse experienced.

Survival Analysis Data Set: All patients who receive BMX-001 will be included in analyses of survival and progression-free survival.

PRO / Cognition Analysis Set: All patients who receive BMX-001 and provide a follow-up assessment will be included in statistical analyses of HRQoL and cognition.

The MTD Analysis dataset as described above is applicable to the Phase 1 portion of this study; whereas, the other datasets are applicable to both the Phase 1 and Phase 2 portions of this study.

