9 SECONDARY OBJECTIVE: COGNITION

The first secondary objective involves an assessment of whether the addition of BMX-001 to standard RT and TMZ treatment for patients newly diagnosed with HGG has an impact upon cognition. The BAC App (provided by VeraSci) and paper forms (HVLT-R, COWA, TMT) were used to assess patient cognition.

BAC App (i-Pad based testing)

The BAC battery of tests was implemented through an iPad-based app called the BAC App (the vendor that provides this is called VeraSci, previously called NeuroCog). Subtests included:

- Verbal Memory
- Digit Sequencing
- Token Motor
- Semantic Fluency
- Letter Fluency
- Symbol Coding
- Tower of London

Beginning at baseline, the BAC will be obtained longitudinally:

- Screening (for the baseline assessment),
- After standard RT and TMZ (within 2 to 4 weeks), and
- Approximately every 8 weeks when a subject returns for a Standard of Care visit during adjuvant TMZ.

Paper cognitive testing

Paper forms were used to assess patient cognition using the following instruments:

- Hopkins Verbal Learning Test-Revised (HVLT-R)
- Trails Making Test Parts A and B (TMT), and
- Controlled Oral Word Association Test (COWA)

Timepoints completed:

- Baseline (prior to the start of RT)
- Standard of care visit before the start of the first cycle of adjuvant temozolomide,
- Standard of care visits that are 6 and 12 months from the completion of radiotherapy/ chemotherapy.

When a subject came off study for disease progression before the approximate 6 and 12 months post completion of treatment timepoint, cognitive testing was supposed to continue and be collected at those timepoints and if present will be included.

The analysis of Cognition data will focus on the cohort of patients who were treated. Typically, patients who were not treated did not provide any cognitive data follow-up.

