9.3 METHOD OF ANALYSIS

For the analysis of change in cognition between baseline and week 24, an analysis of covariance (ANCOVA) will be conducted to compare treatment groups within the treated patient cohort. The outcome of this model is change in cognitive function. Treatment group assignment will be included in the model as a predictor, and the baseline measure of cognitive function will be included as a covariate.

As noted earlier, a significant amount of the follow-up cognitive assessments may be missing due to health decline, disease progression, and death. Much of the missing data is due to a subject permanently dropping out of the longitudinal assessment. A linear random coefficient model stratified by drop-out pattern will assess whether cognitive changes over time are consistent across treatment groups and drop-out patterns. This pattern-mixture model accounts for within subject correlation of longitudinal assessments.

If assumption for conducting either the ANCOVA model or the pattern mixture model are not satisfied, alternative approaches to analyses may be conducted. Options include transformation of the outcome data, as well as use of nonparametric methods.

Given that numerous endpoints will be examined that relate to cognition, adjustments for multiple comparisons (e.g., false discovery rate methods or Bonferroni) may be considered.

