10.3.2 REVISED POWER ANALYSIS

For this endpoint to have relevance, a patients must have received some treatment with temozolomide and radiation in either Arm A or B. At this point, analyses suggest that 78 patients in Arm A and 71 patients in Arm B received protocol treatment. With 78 and 71 patients in Arms A and B, respectively, there is 80% power with a one-tailed chi-square test (α =0.05) to detect a reduction in grade 3 or 4 thrombocytopenia from 15% in Arm B (without BMX-001) to 3.7% in Arm A (with BMX-001).

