15.1 ENDPOINT

Though the study is a longitudinal analysis, the initial focus of the analyses of this objective is an examination of the mean change in HRQoL between baseline and week 24 (occurs after completion of RT) within each treatment arm of the treated subjects.

There is variability in the timing of follow-up measurements. For the purpose of this analysis a +/- 4 week window will define the 24 week assessment.

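### The SAP's Treated Population carries a BMX-001 dose minimum that only Arm A can fail, and the cognition and HRQoL comparisons are specified in treated patients

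*SAP*

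**What the plan says.** SAP section 6 defines the "Treated Population: All patients who completed chemoradiation with or without BMX-001. BMX-001 must be given for at least 6 weeks (or 13 doses". It is the only treated set that the SAP defines. The loading dose plus two doses a week for eight weeks makes 17 planned doses, the number given in protocol 9.1.5.

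- **Cognition.** SAP 9.3 states that "an analysis of covariance (ANCOVA) will be conducted to compare treatment groups within the treated patient cohort". The reason given in section 9 is that "Typically, patients who were not treated did not provide any cognitive data follow-up".
- **HRQoL.** SAP 15.1 examines change to week 24 "within each treatment arm of the treated subjects".
- **Thrombocytopenia.** SAP 10.2 names no population. SAP 10.3.2 says "For this endpoint to have relevance, a patients must have received some treatment with temozolomide and radiation in either Arm A or B" and counts 78 patients in Arm A and 71 in Arm B.
- **Tables.** SAP section 19 lists both ITT and Treated for all three outcomes. For thrombocytopenia, nothing says which set leads.

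The protocol has no dose minimum for these outcomes. Its section 16.1 says "All patients who receive BMX-001 and provide a follow-up assessment will be included in statistical analyses of HRQoL and cognition". Under section 9.1.5, if BMX-001 is discontinued for missed doses, "the patient will remain on the study and all planned study endpoints will be assessed". SAP section 3 gives the SAP precedence where methods differ substantially.

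**The concern.** Take two patients with the same course who both complete chemoradiation. If the Arm A patient stopped BMX-001 early, that patient leaves the set, while the Arm B counterpart stays. The rule depends on tolerance, toxicity and decline after randomisation, so the groups being compared are no longer the groups that were randomised. SAP section 4 singles out cognition and thrombocytopenia among the secondary endpoints, so the affected comparisons matter.

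The stated rationale does not support the rule. Absence of follow-up in untreated patients justifies requiring an assessment, not requiring 13 doses. The drop-out analyses in 9.1 and 9.2 describe patients without assessments. They do not cover patients who have data but too few doses.

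For thrombocytopenia, the exclusion can depend on the outcome itself. Grade 3 thrombocytopenia is a criterion for holding BMX-001 (protocol 13.4.1), and a hold of more than 21 days ends dosing (13.4.3). No BMX-001 hold exists in Arm B.

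**Working it through.** **Dose threshold.** Planned: 1 + 2 × 8 = 17. Minimum: 1 + 2 × 6 = 13, which is 13/17 = 76%. The six weeks and the 13 doses agree with each other, and the threshold is one that patients could miss.

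**The plan's own figures.** Cognition (SAP 9.4.2): SD 30, 52 and 42 patients, two-sided 0.05. The standard error is 30 × √(1/52 + 1/42) = 6.22, and 17.6/6.22 = 2.83. The noncentral t distribution with 92 degrees of freedom gives 79.9% power, so the stated 80% at 17.6 reproduces. Thrombocytopenia (SAP 10.3.2): exact enumeration of the one-tailed Pearson test, 15% against 3.7%, 71 and 78 patients, gives 79.3%, which matches the stated 80%. The same set-ups are used below.

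**Thrombocytopenia illustration.** Assume no treatment effect, with a true rate of 15% in both arms (the Arm B rate in SAP 10.3.2), and start from 78/71. Expected Arm A event patients: 78 × 0.15 = 11.7. If a share e of an arm's event patients is excluded and nobody else, then

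- observed rate = 0.15(1 − e)/(1 − 0.15e)
- remaining set size = n(1 − 0.15e), rounded

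The shares e are assumptions; the documents give none. Rejection probabilities are for a one-tailed test at 0.05 in favour of BMX-001. The Fisher column lets the set sizes vary at random.

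| Event patients lost, A / B | Observed rate, A / B | Set sizes, A / B | Pearson | Fisher |
|---|---|---|---|---|
| 0 / 0 | 15.0% / 15.0% | 78 / 71 | 5.0% | 3.2% |
| 10% / 0 | 13.7% / 15.0% | 77 / 71 | 7.6% | 5.0% |
| 25% / 0 | 11.7% / 15.0% | 75 / 71 | 14.4% | 9.8% |
| 50% / 0 | 8.1% / 15.0% | 72 / 71 | 35.8% | 27.3% |
| 25% / 15% | 11.7% / 13.0% | 75 / 69 | 8.5% | – |
| 25% / 25% | 11.7% / 11.7% | 75 / 68 | 4.9% | – |

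The losses of 10%, 25% and 50% in Arm A correspond to about 1, 3 and 6 patients. With random set sizes the Pearson column reads 5.0%, 7.8%, 14.7%, 36.6%, 8.2% and 5.1%. Equal losses leave the error rate at its nominal level, so the asymmetry drives the result.

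**Reverse direction.** If only 10% of Arm A patients without the event are excluded, the Arm A rate reads 0.15/(0.15 + 0.85 × 0.90) = 0.15/0.915 = 16.4%, and the false-positive rate falls to 3.1%.

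**Cognition illustration.** The shift in the Arm A mean equals the excluded fraction times the gap between kept and excluded patients. Both inputs are assumptions.

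- 10% excluded, gap 15 units: 0.10 × 15 = 1.5 units, 1.5/17.6 = 9% of the detectable difference, two-sided error 5.7%.
- 20% excluded, gap 30 units: 0.20 × 30 = 6 units, 6/17.6 = 34%, two-sided error 15.9%.

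This uses a t-test with SD 30 and 52/42. The ANCOVA adjusts for baseline and would remove whatever part of the gap baseline predicts.

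**The case against.** Several points narrow the concern.

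- Section 19 already lists ITT for all three outcomes, together with a listing of subjects excluded from analysis. An analysis without the dose rule is therefore planned. This stands, but 9.3 and 15.1 still place the comparison in treated patients, and the leading set for thrombocytopenia is not named.
- Sections 9 and 15 use a lower-case 'treated' without citing section 6, and section 9 contrasts these patients with patients who were not treated at all. The looser sense may be intended. That is possible, but section 6 holds the only definition, so the ambiguity itself needs resolving.
- Outcome-driven exclusion for thrombocytopenia needs a long or permanent stop. Protocol 13.4.2 allows re-treatment at 50,000 platelets or above, and missed doses are to be made up. TMZ holds (protocol 11.4) could also stop event patients in either arm from completing chemoradiation, a term the SAP does not define. All of this favours the nearly symmetric rows of the table.
- Under protocol 13.4.3, patients stopped after a hold of more than 21 days are followed for survival without study treatment visits. Dropping the minimum may therefore not recover cognitive data for all of them.
- Protocol 16.1 is an imperfect benchmark: read literally, its PRO/cognition set covers only patients who receive BMX-001, which leaves out Arm B. It does show that no minimum number of doses was intended for Arm A.
- Patients with both cognitive measurements number 52 of 78 (67%) in Arm A and 42 of 71 (59%) in Arm B, which does not show greater loss in Arm A. These figures do not isolate the dose rule.

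These points limit the likely size. None removes the one-arm condition.

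**Conclusion.** The concern holds. As written, the Treated Population applies a post-randomisation exclusion that only Arm A can meet, and the cognition and HRQoL comparisons are specified in treated patients. Thrombocytopenia is tabulated in the same set without a stated leading population, although 10.3.2 sizes it on the 78/71 patients with some treatment.

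The size is unknown because the number of Arm A patients below 13 doses is not given. The illustrated error rates rest on assumed losses, and the larger ones also assume no corresponding loss in Arm B. The direction is plausibly towards BMX-001 but can reverse.

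The main analyses of OS, PFS and response use all randomised patients and are not affected. OS and PFS repeated in the Treated Population carry the same asymmetry. No stated power figure is wrong because of this. It should be fixed before these comparisons are reported.

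**What to change.** 1. Remove the BMX-001 minimum from the set used for the main cognition, HRQoL and thrombocytopenia comparisons.
2. Analyse cognition and HRQoL by assigned arm in all randomised patients with a baseline and the required post-baseline assessment, whatever number of BMX-001 doses they received.
3. Analyse both thrombocytopenia endpoints by assigned arm in patients who started TMZ and RT (the 78/71 set of 10.3.2), and change the section 19 row to match.
4. Align 'treated' in sections 9, 9.3 and 15.1 with these sets, and define what counts as having completed chemoradiation.
5. Keep the 13-dose set as a labelled supportive per-protocol analysis, and report how many Arm A patients it excludes and why.

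The SAP already uses this order for OS and response: ITT first, Treated as an addition. The cost is SAP wording and table shells. Arm A patients with low exposure may slightly dilute the estimated effect, and any set that requires a post-baseline score is still not fully protected by randomisation.
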